9.2 RANDOMIZATION PLAN

In Phase II of this study, a total of 40 participants will be randomized in a ratio of 2:1:1 to placebo, hCT-MSC manufactured at Duke, or hCT-MSC manufactured at Miami. This randomization plan will yield 20 participants on placebo and 10 in each of the hCT-MSC arms. The two hCT-MSC arms will be pooled for analyses comparing treated patients to placebo (see below). The infusion will be blinded so that the medical teams and the patients/LARs will not know which product (placebo, Duke MSC or Miami MSC) the patient receives. There will be unblinded technicians in the laboratories preparing the cells and placebo for infusion, but the final product configuration will be the same for all infusions.

Phase I, Safety 10 patients 1x10^6/kg patient weight (max 100x10^6) Phase II Randomization, Efficacy Placebo hCT-MSCs 10 patients DUKE Fixed dose 100x10^6 10 patients UNIVERSITY OF MIAMI Fixed dose 100x10^6

9.3 ANALYSIS POPULATIONS

Given the differences in design, Phases I and II of the trial will be analyzed separately. All patients who are treated will be analyzed in Phase I. In Phase II the intention-to-treat principle will be adhered to such that participants are analyzed as assigned regardless of whether they receive the assigned treatment or otherwise deviate from the protocol.

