3.3. OBJECTIVES

The Primary Objective of this study is safety of the Investigational Product, hCT-MSCs.

The primary endpoint is safety measured by:

- 1. Incidence of infusion reactions
- 2. Incidence of later reactions attributed to the investigational product Formation of new anti-PRA antibodies

The Secondary Objective of this study is to describe the potential for MSC therapy to favorably alter the course of COVID-ARDS. Endpoints are:

- 1. Time to recovery, defined as discharge from the hospital (alive) or remaining in the hospital without the need for supplemental oxygen or other COVID-related medical care.
- 2. Increase in PaO2/FiO2 ratio by 50% by Day 4 (96 hours after first infusion). PaO2/FiO2 may be calculated from an arterial blood gas or imputed from the SpO2/FiO2 table (Brown, et al. Chest 2016).
- 3. Days to hospital discharge to home
- 4. # of ventilator free days
- 5. # of days requiring O2 support
- 6. Feasibility of accrual to the randomized portion of this study

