4.2. EXCLUSION CRITERIA

- 1. Evidence of multiorgan failure involving one or more organs, excluding the lungs as defined below:
 - a. Presence of shock, defined as MAP < 65 mmHg with signs of peripheral hypoperfusion, or continuous infusion of 2 or more vasopressor or inotrope agents to maintain MAP \geq 65 mmHg.
 - b. Serum bilirubin > 10 mg/dl
 - c. Platelet count < 50,000/ml
 - d. Subjects requiring dialysis as a result of anything other than a COVID-19 infection will be excluded
- 2. Evidence of acquired or congenital immunodeficiency (due to immunosuppressive therapy excluding steroid use for treatment of COVID-19 acute respiratory failure, HIV, previous treatment for cancer, etc.)
- 3. History of metastatic cancer diagnosis or treatment in the past 1 year
- 4. History of previous treatments with MSCs or other cell therapies
- 5. Patient is co-enrolled in any other IND-sponsored clinical trials for COVID-19 or ARDs. Drugs that are administered under emergency use authorizations (EUA) by the FDA are permitted.
- 6. Evidence of pregnancy or lactation
- 7. Moribund patient not expected to survive >24 hours
- 8. Unable/unwilling to deliver lung protective ventilation
- 9. Patient is receiving Extracorporeal Membrane Oxygenation (ECMO)

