5.2.1 DOSE ADMINISTRATION

- Treatment will start within 72 hours from enrollment or when clinically indicated and the subject meets eligibility
- IV placement
- Premedication with each of the following given approximately 30-60 minutes prior to the hCT- MSC infusion:
 - o 12.5-25 mg diphenhydramine IV;
 - 0.5mg/kg hydrocortisone IV
 - Note: if subjects are currently receiving decadron treatment, hydrocortisone may be omitted at the discretion of the PI.
- hCT-MSC infusion, maximum 100 million cells, infused over approximately 30-60 minutes
- Patient monitoring:
 - Vital signs including BP and respiratory rate will be taken every 15 minutes during the infusion and every 30 minutes for one hour after the infusion
 - Pulse oximetry monitoring during and for 1 hour after the infusion
 - Daily monitoring of pulse oximetry and vital signs in between infusions for a minimum of 4 days following the first infusion.

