9.4 ANALYSIS PLAN

Baseline characteristics of the participants will be summarized by study phase. The proportion of patients with infusion-related reactions and other unexpected product- related adverse reactions will be tabulated descriptively using CTCAE terminology. For Phase II, the time to recovery will be described using Kaplan-Meier plots comparing cumulative incidence in participants randomized to hCT-MSC with placebo. Results will be analyzed two ways: combining the two hCT-MSC arms vs. placebo, and each hCT-MSC arm separately vs. placebo. Other continuous, ordinal and binary outcomes will be analyzed in a similar fashion using appropriate descriptive statistics.

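### Section 9.3 gives Phase II one unqualified intention-to-treat rule and no safety set, so read as written the primary safety endpoint keeps never-infused patients in its denominator

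*Combined protocol and SAP*

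**What the plan says.** Section 3.3 makes safety the primary objective. The first measure is "Incidence of infusion reactions"; the others are later reactions attributed to the product and new anti-PRA antibodies.

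Section 9.3 defines the analysis populations. For the open-label part: "All patients who are treated will be analyzed in Phase I". For Phase II, under the intention-to-treat principle, "participants are analyzed as assigned regardless of whether they receive the assigned treatment or otherwise deviate from the protocol". The Phase II rule is not limited to efficacy, and no second Phase II population appears there or elsewhere.

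Section 9.4 describes the safety analysis: "The proportion of patients with infusion-related reactions and other unexpected product- related adverse reactions will be tabulated descriptively using CTCAE terminology". It names no denominator. Antibodies are not mentioned, so they fall under the general sentence on other binary outcomes.

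Section 9.2 gives the arm sizes: "This randomization plan will yield 20 participants on placebo and 10 in each of the hCT-MSC arms". Section 5.2.1 allows a gap before treatment: "Treatment will start within 72 hours from enrollment or when clinically indicated and the subject meets eligibility". Section 6.1.1 measures PRA at baseline and Day 28 only.

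**The concern.** Analysis as assigned is the right default for recovery and survival. It does not suit reactions to an infusion, because a patient who was never infused cannot have one. Including that patient can only lower the reported rate in the arm concerned.

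Several provisions make uninfused patients possible. Treatment may start up to 72 hours after enrolment and depends on the patient still being eligible (5.2.1). On expected survival, entry bars only a "Moribund patient not expected to survive >24 hours" (4.2), a shorter horizon than that window. Withdrawal is allowed at any time (4.3). Non-infusion also need not be balanced between arms: the Duke product has a post-thaw viability specification of at least 70% (3.4), and the placebo has no cells to fail such a test.

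Two further consequences follow from the same rule. If the wrong product is infused, any reaction is tabulated under a product the patient did not receive. And a patient who dies before the Day 28 PRA sample cannot show a new antibody but remains in the denominator.

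At stake is the accuracy of small safety proportions on the primary endpoint, particularly if they are shown separately for the two cell products.

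**Working it through.** **The plan's own safety figure.** Section 9.1.1 gives the probability of at least one reaction in 10 treated patients as 0.65, 0.94 and 0.98 at rates of 0.10, 0.25 and 0.33. With 1 − (1 − p)^10 these are 0.6513, 0.9437 and 0.9818, so they reproduce. The calculation counts patients who are treated, which is the denominator that 9.3 does not carry into Phase II.

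**Dilution of reaction rates.** Inputs: N = 20 in the pooled cell arm and N = 10 per product (9.2); k = patients never infused, which the documents do not give and which is varied here.

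Reported rate = rate among infused × (N − k)/N, a relative understatement of k/N. One patient is 1/20 = 5% in the pooled arm and 1/10 = 10% in a product arm.

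| Rate among infused | N = 20, k = 1 | N = 20, k = 2 | N = 20, k = 4 | N = 10, k = 1 |
|---|---|---|---|---|
| 10% | 9.5% | 9.0% | 8.0% | 9.0% |
| 25% | 23.75% | 22.5% | 20.0% | 22.5% |
| 33% | 31.4% | 29.7% | 26.4% | 29.7% |

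As counts: one reaction among 9 infused is 11.1% but appears as 1/10 = 10.0%. Two among 18 infused is 11.1% but appears as 2/20 = 10.0%.

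**How many might go uninfused.** Section 2 quotes ARDS mortality of 30–60% without a time horizon. Assume that it applies over 28 days and that every patient waits the full 72 hours after randomisation.

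- Deaths spread evenly: (3/28) × 0.30 = 3.2% and (3/28) × 0.60 = 6.4%. Times 40, this is 1.3 to 2.6 patients, or 0.3 to 0.6 per arm of 10.
- Constant hazard: 1 − 0.70^(3/28) = 3.7% and 1 − 0.40^(3/28) = 9.4%. Times 40, this is 1.5 to 3.7 patients, or 0.4 to 0.9 per arm of 10.

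Shorter waits give fewer. Withdrawal and loss of eligibility would add to these, but the documents give no basis for a figure.

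**Antibodies.** Section 3.6 reports Phase I deaths on days 7 and 27, among others. The first precludes a Day 28 sample. The second may or may not, since 6.1.2 allows two days either side. So 1 or 2 of 10 lacked the sample through death. At that proportion, 2 to 4 of 20 pooled patients would lack it, and a 10% rate among those sampled would appear as 10% × 18/20 = 9% to 10% × 16/20 = 8%. If the 30–60% mortality applied by Day 28 (assumed), 6 to 12 of 20 would lack it, and 10% would appear as 10% × 14/20 = 7% to 10% × 8/20 = 4%.

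**The case against.** The strongest reply is that 9.3 never says its rule covers every analysis and does not name the safety endpoint. Section 9.4 leaves the denominator open, and a sensible team would count only infused patients for infusion reactions. That is fair as a prediction of what might be done. It does not alter the text: the one Phase II rule is unqualified, no other population exists to fall back on, and the sentence before it shows that a treated-patient set was written for Phase I only.

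The size is also open to challenge, and much of this stands. The 72 hours run from enrolment, and no section says where randomisation falls in that window; if it is close to infusion, few randomised patients will go uninfused. In Phase I all 10 patients were treated and the earliest death was on day 7. That is weak evidence, because the cohort may have been filled with treated patients, but it does not suggest heavy early loss.

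A reader might infer more than the documents support:

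- That two of 10 in a product arm would typically go uninfused. The expected pre-infusion deaths above are 0.3 to 0.9 per arm of 10, and only after a full 72-hour wait.
- That confidence limits would come out too favourable. None are planned; 9.4 is descriptive.
- That stopping decisions would be affected. The rules in 8.4 are event counts with no denominator.
- That Phase I and Phase II rates were meant to be compared directly. Section 9.3 analyses the phases separately, and their dosing basis differs.
- That separate Duke and Miami safety tables are certain. The two-way analysis in 9.4 directly follows time to recovery, so its extension to safety is an inference.

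Wrong-product infusion is hypothetical, and no rate is given for it.

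**Conclusion.** The point holds in a limited form. Section 9.3 states a rule that, applied as written, puts never-infused patients in the denominator of the primary safety endpoint, and nothing else in the protocol supplies a Phase II safety set. Within an arm the bias runs only towards lower reaction rates. The contrast with placebo could move either way if non-infusion is unbalanced.

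The size is modest and conditional on at least one randomised patient not being infused: 5% relative per patient in the pooled arm and 10% in a single-product arm, which is 0.5 and 1.0 percentage points at a 10% rate. The pre-infusion death estimates of 1.3–2.6 or 1.5–3.7 of 40 rest on an assumed 28-day mortality and an assumed full wait after randomisation, and should be read as upper-end illustrations. The antibody denominator does not depend on when randomisation occurs, because early deaths leave no Day 28 sample in any case. This is a cheap improvement, not a flaw that threatens the trial.

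**What to change.** In Section 9.3:

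- Add a Phase II safety set: all patients in whom at least one infusion was started, grouped by the product actually received (placebo, Duke, Miami). Use it for infusion reactions and product-attributed reactions.
- For new anti-HLA antibodies, use members of that set with both baseline and Day 28 samples, and state how many lack them.
- Keep intention-to-treat for recovery, survival and the other efficacy outcomes.

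In Section 9.4, name the safety set as the denominator and add a table of how many randomised patients received 0, 1, 2 and 3 infusions, with reasons.

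The cost is a few sentences and one table, with no change to trial conduct. Safety denominators become slightly smaller. The antibody result will describe mainly patients who survive to Day 28, which is why the number without paired samples must be shown beside it.

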9.4 ANALYSIS PLAN

Baseline characteristics of the participants will be summarized by study phase. The proportion of patients with infusion-related reactions and other unexpected product- related adverse reactions will be tabulated descriptively using CTCAE terminology. For Phase II, the time to recovery will be described using Kaplan-Meier plots comparing cumulative incidence in participants randomized to hCT-MSC with placebo. Results will be analyzed two ways: combining the two hCT-MSC arms vs. placebo, and each hCT-MSC arm separately vs. placebo. Other continuous, ordinal and binary outcomes will be analyzed in a similar fashion using appropriate descriptive statistics.

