3.6. CLINICAL EXPERIENCE WITH HCT-MSC

The current hCT-MSC product manufactured at Duke has been used in >90 children given >160 doses of 12-6 million hCT-MSC/kg intravenously, in approximately 54 adults with OA of the knee at 10-20M cells/dose given directly into the knee joint, and in 1 adult with bronchiectasis under an IND at a dose of 100 million total cells. In the proposed Phase 1 pilot portion of this study, we capped the dose per infusion at 100 million cells (total absolute dose) to follow conventions in an ongoing trial where absolute doses of 200 million cells appeared less effective than 100 million cells.

Confidential Page 13 of 32

The first 10 patients enrolled in this study were enrolled on the Phase 1, open label portion of this study. That cohort was fully enrolled with 8 patients treated at DUMC and 2 patients treated at the Boca Raton Regional Hospital. The median age of the patients was 61.5 years (29-79 years), 70% were female, 60% were Caucasian, and 30% were Hispanic. There were 4 SAEs reported in the trial, all resulting in death occurring on days 7, 27, 39, and 344 on study. None were deemed related to the MSC product. The MSC product infusions were well tolerated. There were no infusion related AEs or SAEs.

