3.6.1 SAFETY

All patients will be pre-medicated before each dose of hCT-MSCs with a parenteral dose of diphenhydramine (12.5-25mg) and hydrocortisone 0.5 mg/kg IV approximately 30-60 minutes prior to infusion. Using this approach, infusion- associated reactions are uncommon (<1%) and mild. Observed reactions consist of, rash, bronchospasm and rarely, transient hypotension. If an adverse event occurs after the first or second dose, the subsequent doses will not be administered.

The following adverse events, deemed *not related* to the MSC product have been reported in patients receiving BM-MSCs for treatment of graft versus host disease following a blood or marrow transplant where more than 1,000 adults have been treated: increased blood pressure, low blood pressure, difficulty breathing, pain in the abdomen or stomach, abdominal distension, bleeding in the gastrointestinal tract, swelling in legs or arms, nausea, vomiting, diarrhea, dizziness, itching, rash, fever, elevation of blood cells (eosinophils), increase in blood levels of various laboratory values (including alkaline phosphatase, creatinine, lactate dehydrogenase, alanine transaminase and glucose), hypocalcemia, ascites, kidney impairment, hepatomegaly, neutropenia, thrombocytopenia graft versus host disease, chest discomfort, chest pain, oral yeast infection, muscle weakness, joint pain, back pain, cold sweat, headache, and depression.

Other theoretical risks include engraftment and differentiation of transplanted MSCs with ectopic tissue formation. In addition, MSCs in the paracrine and endocrine systems may promote tumor growth and metastasis by diminishing or suppressing the antitumor immunity and inducing neovascularization.

Long term safety information of the use of MSCs is still unknown, but 10 year follow-up in hundreds of treated patients has not revealed any serious problems to date.

Risks associated with the use of diphenhydramine include dizziness, sedation, dry mucous membranes, dryness of the nose and throat, and thick sputum. Allergic reaction can occur, which would, include swelling of the throat and trouble breathing.

Possible side effects of corticosteroids include fluid retention and weight gain, muscle weakness, peptic ulcer; high blood pressure; permanent changes in the bones; increase in infection risk and hyperglycemia.

Confidential Page **14** of **32**

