8.2.3 EXPECTEDNESS

Expected events are those that have been previously identified as resulting from administration of the investigational agent. An adverse event is considered unexpected, for expedited reporting purposes only, when either the type of event or the severity of the event is not listed in the current Product Label.

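### The safety table in section 9.4 counts only 'unexpected' later product-related reactions, whereas the primary endpoint in section 3.3 counts every later reaction attributed to the product

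*Combined protocol and SAP*

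**What the plan says.** All references are to the combined protocol and SAP.

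- **Section 3.3 (Objectives)** measures the primary safety endpoint by "Incidence of infusion reactions" and "Incidence of later reactions attributed to the investigational product", and then names new antibody formation. Expectedness is not mentioned.
- **Section 9.4 (Analysis Plan)** has one sentence on safety, which says that the proportion of patients with "infusion-related reactions and other unexpected product- related adverse reactions will be tabulated descriptively using CTCAE terminology". It then describes time to recovery, gives the pooled and separate comparisons with placebo, and closes by extending descriptive analysis to other continuous, ordinal and binary outcomes. AEs and SAEs regardless of attribution are not named.
- **Section 8.2.3 (Expectedness)** calls events expected if they were already identified as resulting from the agent. It says when an event is unexpected "for expedited reporting purposes only", judged against a product label.
- **Sections 8.1.1, 8.2.2 and 8.3** define AEs whether or not related, have the treating physician judge causality for each collected AE, and follow SAEs and survival to 90 days. Section 8.1.1 keeps events unequivocally due to disease progression out of AE reporting unless they are considered product-related.
- **Section 9.2** gives Phase II 20 placebo, 10 Duke and 10 Miami patients, with medical teams and patients blinded.

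**The concern.** Safety is the primary objective, and the table in 9.4 is the only place where the plan says how the reaction endpoint will be summarized. If that table applies a condition that the endpoint does not have, the reported incidence can fall below the defined incidence, and a reader of the results could not tell. The condition is also borrowed from regulatory reporting, where it decides which reports are expedited. It does not say whether a reaction occurred.

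A second question is whether Phase II uses its placebo arm for safety. With blinded randomization, event rates can be compared without anyone deciding what caused each event. A table restricted to product-related events depends on that decision in patients with ARDS, whose illness offers competing explanations.

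**Working it through.** **Step 1. Endpoint against table.**

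| Component | Section 3.3 | Section 9.4 |
|---|---|---|
| Infusion reactions | all | all |
| Later, product-attributed, unexpected | counted | tabulated |
| Later, product-attributed, expected | counted | not tabulated |
| Later, not product-attributed | not counted | not tabulated |

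The only disagreement is in the third row, and it comes from the word 'unexpected'. 'Product-related' in 9.4 and 'attributed' in 3.3 select the same way. The antibody component is not in the safety sentence of 9.4; the closing sentence may cover it, and it is left aside here.

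**Step 2. Is there a reason to apply the filter in analysis?** Section 8.2.3 limits its definition of 'unexpected' to expedited reporting, and no other definition is given. So 9.4 either uses a reporting definition outside its stated purpose or uses an undefined term.

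**Step 3. The plan's own safety figures.** Section 9.1.1 gives the chance of at least one product-related reaction in 10 patients as 1 − (1 − p)^10:

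- p = 0.10: 0.651 (plan: 0.65)
- p = 0.25: 0.944 (plan: 0.94)
- p = 0.33: 0.982 (plan: 0.98)

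These reproduce. They refer to product-related reactions without an expectedness condition, so the Phase I sample-size rationale agrees with 3.3 rather than with 9.4.

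**Step 4. How much could the filter matter?** Let f be the share of product-related reactions that stay in the 9.4 table, because they are either infusion-related or unexpected. The documents give no value, so f is an assumption anywhere from 0 to 1. The chance that the table shows at least one reaction is 1 − (1 − p·f)^10:

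| f (assumed) | p = 0.10 | p = 0.25 | p = 0.33 |
|---|---|---|---|
| 1 | 0.65 | 0.94 | 0.98 |
| 0.75 | 0.54 | 0.87 | 0.94 |
| 0.5 | 0.40 | 0.74 | 0.84 |
| 0.25 | 0.22 | 0.48 | 0.58 |
| 0 | 0 | 0 | 0 |

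If nearly all reactions are infusion-related, or nearly all later ones are unexpected, f is close to 1 and little changes. The table shows what follows from each assumption; it is not an estimate of undercounting.

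**Step 5. What could an attribution-free Phase II table show?** With n = 20 per arm, mean proportion p̄ and two-sided 5% error, approximate power is Φ[(|p₁ − p₂| − 1.96·√(2p̄(1 − p̄)/n)) / √((p₁(1 − p₁) + p₂(1 − p₂))/n)].

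- Assumed 30% against 60%: (0.30 − 1.96 × 0.157)/0.150 ≈ −0.06, power about 48%.
- Assumed 20% against 40%: (0.20 − 1.96 × 0.145)/0.141 ≈ −0.59, power about 28%.

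Such a table is therefore descriptive, in line with section 9.1.2.

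**The case against.** The strongest reply is that the filter may remove nothing. Section 3.6.1 says of infusion-associated reactions: "Observed reactions consist of, rash, bronchospasm and rarely, transient hypotension". Infusion reactions enter the 9.4 table unfiltered. A reader might infer that these known reactions would be lost; the documents do not support that, because they describe none of them as a later reaction. Nor do they name any later reaction already established as caused by the product, so most later attributed reactions might well be unexpected. This stands, and it limits the point to a mismatch of definition with unknown effect. It does not justify the word: what counts as expected can grow with experience, and the endpoint does not depend on it.

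A reader might also point to Phase I: "There were 4 SAEs reported in the trial, all resulting in death occurring on days 7, 27, 39, and 344 on study". None was deemed related, so the 9.4 safety sentence covers none of the four. That is not undercounting of the 3.3 endpoint. Unrelated deaths are outside that endpoint, and deleting 'unexpected' would not bring them in. Likewise, one patient in an arm of 20 is 1/20 = 5 percentage points, but this only restates the arm size and does not show that any patient would be dropped.

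Finally, a reader might infer that a treatment difference in events ascribed to ARDS could appear nowhere. That goes too far. Day-28 survival is a key secondary endpoint in the synopsis, oxygenation and ventilator outcomes are listed in 3.3, and the closing sentence of 9.4 can cover them. The DSMB may also request unblinded data (section 10.3). What remains is that other AEs and SAEs judged unrelated are not named in any tabulation. Section 3.3 does not promise such a table, so its absence is a missed opportunity rather than an error.

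**Conclusion.** The point holds in a limited form. Section 9.4 puts an expectedness condition on later reactions that the primary endpoint in 3.3 does not have and that 8.2.3 assigns to expedited reporting. The two sections should agree, because this is the primary endpoint. The size of the effect is unknown: it is zero if no later attributed reaction is expected, and it grows with the share that is. The conclusion rests on the wording alone and assumes that 9.4 would be followed as written.

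The missing by-arm table of AEs and SAEs regardless of attribution is an improvement worth making, given 20 blinded placebo patients. It would be descriptive and would not settle causality. The product-label reference in 8.2.3, for an agent studied under IND, is a secondary clarification of reporting.

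**What to change.** 1. In 9.4, delete 'unexpected', so that the table covers every infusion reaction and every later reaction attributed to the product, as in 3.3.
2. For Phase II, add a descriptive table by arm (pooled hCT-MSC, Duke, Miami, placebo) of all collected AEs by CTCAE grade and all SAEs, regardless of attribution or expectedness. Show product-attributed reactions as a subset.
3. Give all-cause deaths a separate row. An AE table alone would miss some of them, because 8.1.1 keeps unequivocal disease progression out of AE reporting.
4. List all SAEs and deaths for Phase I with day of onset and attribution. The day-344 death lies beyond the 90-day follow-up in 8.3 and should be marked so.
5. In 8.2.3, name the reference safety document that applies to the investigational product, and keep expectedness for expedited reporting.

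The cost is a few words in two sections, one table and one listing, using AE, SAE and survival data that the protocol already collects. The downside is a longer table with many disease-related events in both arms, which needs a note that it is descriptive. No treatment or follow-up procedure changes.
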